 - All adverse events that manifest after administration of the investigational product shall be collected.
 - At Visits 3, 4, and 5 (2nd, 3rd, and 4th administration sessions of the investigational product), adverse events shall be assessed and collected before and after administration of the investigational product.
- (2) Laboratory tests (complete blood cell count/general blood chemistry/urinalysis tests)
- (3) Vital signs

Secondary endpoint

Considering that CMT1A (Charcot-Marie-Tooth) disease is a rare disease that has no treatment yet, this clinical trial is designed to evaluate clinically meaningful factors in relation to efficacy.:

- (1) Change in severity of disease
 - CMTNS-v2 (Charcot-Marie-Tooth Neuropathy Score version 2)
 - FDS (functional disability scale)
- (2) Changes in lower limb function
 - ONLS (overall neuropathy limitation score) leg scale
 - 10MWT (10-meter walk test)
- (3) Changes in fatty infiltration level of lower limb muscles
 - MRI leg
- (4) Nerve regeneration potential
 - CMAP (compound motor nerve action potential)

- SNAP (compound sensory nerve action potential)
- NCV (nerve conduction velocity)
- (5) HGF antibody generation by VM202

Statistical analysis of primary endpoint

Definition of subjects for primary endpoint analysis

Safety set

Of all subjects who were decided suitable during screening, the analysis includes those who were administered the investigational product and can be assessed for safety. The study subjects included in the safety and tolerability analysis are analyzed based on information on the investigational product that was actually administered. Furthermore, the safety set is analyzed for demographic data (gender, age, etc.) and background factors (medical history, previous drug treatment, etc.)

Statistical analysis method for primary endpoint

(1) Adverse event:

: Summary and analysis of adverse events are conducted on Treatment-Emergent Adverse Events (TEAEs) that occur after the administration of the investigational product.

Frequency and percentage of TEAEs, adverse drug reactions (ADRs), and serious adverse events (SAEs), occurring after investigational product administration, are provided.

TEAEs, ADRs, and SAEs are coded using MedDRA (Medical Dictionary for Regulatory Activities, latest version) according to the System Organ Class (SOC) and Preferred Terminal (PT). The number of subjects with coded adverse events, the occurrence rate, and the number of the cases are presented.

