The formation of anti-HGF Ab in the blood is checked. Preliminary assessment is made of whether antibody production is correlated between the subject group who are considered to have increased muscle mass and improved function and those who are not. The summary table presents the frequency and ratio of antibody generation in the blood.

However, if no antibody in the blood is produced in any single subject, no results are presented.

For the secondary endpoint, for values before and after treatment, continuous variables present average, standard deviation, median value, minimum value, and maximum value; categorical variables present frequency and percentage. To compare differences of values before and after treatment, continuous variables use a paired t-test or Wilcoxon sign rank test; categorical variables use McNemar's test.

Small group analysis

When conducting the adverse events and efficacy assessments, small group analysis is carried out considering the following items:

- Gender (male, female)
- Age (≤ median, > median)
- Baseline BMI (≤ median, > median)
- Presence or absence of medical history
- Presence or absence of concomitant medications
- Disease severity (CMTNS v2) (mild, moderate)

If the number of subjects that fit into the above subgroups is small in each group, the analysis shall not be conducted on that subgroup. For example, if male subjects are less than 30% of the total subjects, no analysis is performed on gender and whether to analyze shall be determined in a data review meeting prior to datalock.

Retrospect ive biomarker study(To be conducted separately)

PRT NO: VMCMT-001 **Confidential** 2021.06.07 11 / 12

Summary of study schedule

Schedule	Day - 30 to Day - 1	Day -1	Da	ay O	Day 14 ± 5		Day 30 ± 7			Day 104 ± 7		Day 180 ± 7	Day 270 ± 7		
Visit No.	Vieit 1		Visit 2 (Hospitalization)		Visit 3		Outpatient follow-up if	VISIL 4		Visit 5		Visit 6	Visit 7	Early Term	Unsche
Specific Notes	Scree ning	Hospitali zation Day ¹⁵⁾		istration After Administ ration ¹⁶⁾	Admini Befor e	stration After Administ	abnormal test results are present on Day 14 (Second Administrati on)*		istration After Administ ration ¹⁶⁾		urth istration After Administ ration ¹⁶⁾	Outpati ent Follow- up	Outpati ent Follow- up	inati on	duled Visit
Informed consent form	Х														
Subject background survey ¹⁾	Х			5					-						
Medical history survey ²⁾	Х														7(
Physical examination ³⁾	X														

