: Descriptive statistics (mean, standard deviation, median, minimum, maximum) shall be presented for the changes in nerve conduction studies (CMAP, SNAP, NCV) at the termination visit (V7) compared with the baseline (V2), and analysis shall be performed for the differences before and after administration by using a paired t-test (Wilcoxon signed rank test if the assumption of normal distribution is not satisfied).

(5) HGF antibody production by Engensis (VM202)

The presence or absence of HGF antibody (anti-HGF Ab) in blood shall be verified with the ELISA method. A preliminary assessment shall be performed on whether antibody production is correlated between the subject group determined to have increased muscle mass and improved function, and the subject group not determined as such.

However, if antibodies in blood were not produced in any of the subjects, the results shall not be presented.

: Descriptive statistics (frequency, percentage) shall be presented for the changes in HGF antibody production at the termination visit (V7) compared with the baseline (V2). A contingency table shall be prepared for the differences before and after administration, and analysis shall be performed using the McNemar's test.

9. Document Management

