#### (5) HGF antibody production by Engensis (VM202)

The presence or absence of HGF antibody (anti-HGF Ab) in blood was verified with the ELISA method. A preliminary assessment was performed on whether antibody production is correlated between the subject group determined to have increased muscle mass and improved function, and the subject group not determined as such.

However, if antibodies in blood were not produced in any of the subjects, the results were not presented.

The antibody test for hepatocyte growth factor was performed at Visit 2 (Day 0) and Visit 7 (termination visit, Day 270) (performed prior to administration at Visit 2 [Day 0]).

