#### 4.7 Safety and Tolerability Assessments

#### (1) Adverse events

Summarization and analysis of adverse events shall be performed on treatment-emergent adverse events (TEAEs).

The number of subjects, percentages, 95% confidence interval (Clopper-Pearson Confidence Interval), and number of cases shall be presented for treatment-emergent adverse events (TEAEs), adverse drug reactions (ADRs), adverse events of special interest (AESIs), and serious adverse events/adverse drug reactions (SAEs). In addition, the number of subjects, incidence, and number of cases shall be presented for SAE status of adverse events, SAE reason, severity, causal relationship to the investigational product, relationship to the IP administration procedure, relationship to underlying disease, actions related to the investigational product, corrective treatments, outcomes, etc.

The adverse events, adverse drug reactions, and serious adverse events shall be encoded using the system organ classes (SOCs) and preferred terms (PTs) by using the medical dictionary for regulatory activities (MedDRA, V24.0). The number of subjects with onset, the incidence, the number of cases, etc., shall be presented for the encoded adverse events. In addition, a detailed list shall be presented if serious adverse events occur.

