#### (5) HGF antibody generation by VM202

: Descriptive statistics (frequency, percentage) shall be presented for the HGF antibody production at the termination visit (DAY 270) compared with the baseline (DAY 0). A contingency table shall be prepared for the differences at the termination visit compared with the baseline, and analysis shall be performed using the McNemar's test.

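### Protocol and SAP both say anti-HGF antibody results are not presented if no subject produces antibody; the rule's scope is unclear, and read plainly it withholds a zero result for a listed secondary endpoint

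*Protocol*

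**What the plan says.** The synopsis and Protocol 5.1 both list the endpoint among the secondary items, as "5) HGF antibody generation by VM202". The schedule in Protocol 6.1 marks the sample at Day 0, Day 270 and Early Termination.

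The non-presentation rule appears three times:

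- **Protocol synopsis, secondary endpoint item (5).** A table is promised first: "The summary table presents the frequency and ratio of antibody generation in the blood". Then comes the exception: "However, if no antibody in the blood is produced in any single subject, no results are presented". The next paragraph sets a general rule for all secondary endpoints: frequency and percentage for categorical variables, with McNemar's test for the before-after comparison.
- **Protocol 8.4.4(5).** After the sentence on a preliminary correlation with clinical improvement: "However, if antibodies in blood were not produced in any of the subjects, the results shall not be presented". The analysis line follows directly and begins: "Descriptive statistics (frequency, percentage) shall be presented for the changes in HGF antibody production at the termination visit (V7) compared with the baseline (V2". McNemar's test and a contingency table are then required.
- **SAP 3.3(5).** Again after the correlation sentence: "However, if antibodies in blood were not produced in any of the subjects, the results were not presented".

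SAP 4.8(5), which specifies the analysis, does not mention the exception. It begins "Descriptive statistics (frequency, percentage) shall be presented for the HGF antibody production at the termination visit (DAY 270" and goes on to the comparison with Day 0, a contingency table and McNemar's test.

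**The concern.** A reporting rule should not depend on the result it governs. Read plainly, this one means that a secondary endpoint is tabulated if at least one subject is positive and left out if none is. The reader would then have neither a numerator nor a denominator and could not tell how many subjects were tested.

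The denominator cannot be assumed to be 12. Missing values after early termination are not imputed (Protocol 8.2, SAP 4.3), and the analysis lines name only the termination visit, although the schedule also collects a sample at Early Termination.

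The protocol files this endpoint under efficacy (6.2), but antibody against the expressed protein also bears on safety. Protocol 3.6 says that the expressed HGF is identical to the protein produced in the body, and the product is given four times. The safety relevance is my inference; the documents do not state it. A zero result is also foreseeable: Protocol 3.8 reports that no antibodies to the expressed HGF were produced in the earlier nine-subject angina study.

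**Working it through.** **1. Scope of the exception.** The passages side by side:

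| Place | Exception stated? | Sentence before it | What follows it |
|---|---|---|---|
| Synopsis, item (5) | Yes | Frequency table | General rule: frequency, percentage, McNemar |
| Protocol 8.4.4(5) | Yes | Correlation | Frequency, percentage, table, McNemar |
| SAP 3.3(5) | Yes | Correlation | Visit days of the test |
| SAP 4.8(5) | No | – | Frequency, percentage, table, McNemar |

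Two readings are open. On the narrow reading, only the correlation lapses when nobody is positive, and the frequencies are still shown. On the wide reading, nothing is shown. The word *results* is unqualified in all three places, which favours the wide reading. The unconditional lines that follow favour the narrow one. A programmer with no positive subjects could defend either output.

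**2. What a zero count would carry.** The plan states no antibody rate, precision target or confidence limit, so there is no plan figure to reproduce. Inputs:

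- n = 12 subjects (Protocol 5.3.1, SAP 1.4.1).
- Two-sided 5% level (Protocol 8.4.1), so 0.025 in each tail.
- Clopper-Pearson method. SAP 4.7(1) names it for adverse events: "95% confidence interval (Clopper-Pearson Confidence Interval), and number of cases shall be presented for treatment-emergent adverse events (TEAEs". No interval is planned for antibody, so using it here is my addition.

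For 0 events in n, the exact two-sided upper limit is 1 − 0.025^(1/n):

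- n = 12: 1 − 0.025^(1/12) = 0.2646, or 26.5%
- n = 11: 0.2849, or 28.5%
- n = 10: 0.3085, or 30.8%

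The rows for 11 and 10 assume one or two subjects without a post-treatment result. The documents do not give that number.

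**3. How often zero would occur with a non-zero true rate.** P(0 of 12) = (1 − p)^12, at assumed true rates:

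| Assumed true rate p | P(0 of 12) |
|---|---|
| 5% | 0.95^12 = 54% |
| 10% | 0.90^12 = 28% |
| 15% | 0.85^12 = 14% |
| 20% | 0.80^12 = 7% |

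**4. McNemar's test with no positives.** With b and c the two discordant counts, the statistic is (b − c)²/(b + c). If nobody is positive at either visit, b = c = 0, the statistic is 0/0 and the exact p-value is 1. The planned test therefore adds nothing in this case. That is a reason to omit the test, but not the count.

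**The case against.** The strongest case against is that the rule was fixed in advance and is stated openly in both documents. An omitted table would itself tell an informed reader that nobody was positive, and this is not selection after seeing the data. The sponsor stated an earlier nil finding openly in Protocol 3.8, and the wording may be loose translation. All of this stands as a reason not to read intent into the sentence. It does not supply the number tested, and a reader of the results without the plan could not tell a zero from an analysis that was never done.

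It is also fair to say that the 26.5% limit does not measure the defect. It would apply to any zero count in 12 subjects. I use it only to show what a reported zero would convey.

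A reader might infer a stronger point: that the synopsis suppresses the result while the protocol body and SAP require it without exception. The documents do not support this. Protocol 8.4.4(5) and SAP 3.3(5) contain the same exception, and the synopsis also follows it with a general frequency rule. The one difference is that the synopsis puts a frequency sentence before the exception as well. The ambiguity is shared, and only SAP 4.8(5) is silent.

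**Conclusion.** The concern holds as a reporting-rule problem common to protocol and SAP. Three places state a rule whose plain wording withholds a listed secondary endpoint when the count is zero. The surrounding analysis lines require the count without saying whether the exception applies to them.

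What would be lost is the n/N of subjects tested. With all 12 evaluable and none positive, the omitted line would be 0/12, 0% (exact 95% CI 0% to 26.5%). Such a result does not show that antibody formation is absent. The interval rests on the target sample size and on the interval method that the SAP uses for adverse events; the true rates of 5% to 20% are assumptions. The finding touches neither the primary endpoint nor the design. It deserves correction because the rule depends on the outcome and the correction is very cheap.

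**What to change.** 1. In the synopsis item (5), Protocol 8.4.4(5) and SAP 3.3(5), delete the non-presentation sentence, or replace it with: *The correlation assessment and McNemar's test are not performed if no subject is positive.* Editing the synopsis alone would leave the rule in force in the other two places.
2. In Protocol 8.4.4(5) and SAP 4.8(5), state that antibody positivity is always reported as n/N at Day 0 and after treatment, whatever the result. N is the number of subjects with a result at that time point. Show Day 270, and display any Early Termination samples separately.
3. Give the Clopper-Pearson 95% confidence interval beside each percentage, as SAP 4.7(1) already does for adverse events.

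The cost is one sentence in three places, a clarified analysis line in the protocol and SAP, and one interval in a table already planned. No new samples, assays or visits are needed, and completed enrolment (Protocol 5.7.1) is no obstacle.

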3.1 Incidence and Prevalence of Charcot-Marie-Tooth Disease

Hereditary neuropathy includes a variety of peripheral neuropathies that are clinically and genetically different. Charcot-Marie-Tooth disease (hereinafter CMT), also known as hereditary motor and sensory neuropathy (HMSN), is the most common disease of these hereditary neuropathies. The prevalence of CMT is approximately 1 person in every 2,500.[1]

It is known that there are approximately 2.9 million patients worldwide, and the number of patients in South Korea is estimated to be approximately 20,000. CMT is divided into several subtypes, and the most common is CMT subtype 1A (hereinafter CMT1A), the target disease of this clinical study, which accounts for 40% of all CMT. There are approximately 9,000 patients with CMT1A in South Korea, and 1.4 million CMT1A patients worldwide. CMT1A is caused by the duplication of the PMP22 gene.[2]

3.2 Pathophysiology of Charcot-Marie-Tooth Disease

CMT is a hereditary peripheral neuropathy, which is a disease caused by damage to motor and sensory nerves by gene mutations. Various clinical patterns are shown depending on the causative gene, and clinical symptoms such as amyotrophy in the upper and lower limbs, foot deformity, sensory loss, blindness, hearing loss, and areflexia are commonly observed, which show a pattern of gradually progressing over time.[3]

The peripheral nervous system (PNS) extends out from the central nerves (brain, spinal cord) and is distributed to each part of the body. It serves the role of transmitting external stimuli to the central nervous system and delivering commands of the central nervous system to muscles or each organ. The peripheral nervous system is generally divided into the somatic nervous system and the autonomic nervous system. The somatic nervous system is further divided into motor and sensory nerves. Motor nerves are efferent, and they induce muscle contraction by transmitting excitation from the center to the periphery (skeletal muscles). Sensory nerves are afferent, and they induce sensation by transmitting signals from the periphery (sensory organs) to the center. Peripheral nerves that emanate from the central nerves gradually divide and spread throughout the body to reach the peripheral organs, which are divided into the cranial nerves (12 pairs) and the spinal nerves (31 pairs) depending on where they emanate from.

Each axon within the peripheral nerves exists inside a type of tube made of myelin sheaths produced by special neuroglia called Schwann cells. An axon and myelin sheaths combined are called a nerve fiber. A number of nerve fibers form a bundle to constitute one nerve, but the number of nerve fibers varies. Approximately 1/3 of all nerve fibers are wrapped quite well. In the growth phase, Schwann cells wrap around an axon in several layers. This results in the formation of a myelin sheath made of a mixture of lipids and proteins in between the axon

and the Schwann cells. As such, a cross-section of a nerve fiber resembles an electrical wire surrounded by a thick insulation layer. A nerve fiber insulated in this way is called a myelinated or medullated fiber. The nerve conduction velocity of a myelinated nerve fiber is much faster than that of an unmyelinated nerve fiber.

CMT can be largely classified into two types based on nerve conduction studies and histological features, and these are CMT1 characterized by demyelination and CMT2 characterized by damages to axon cells. Recently, more detailed classifications have become possible as more studies on the causative gene have become active due to advances in molecular genetics technology. With over 90 genetic mutations discovered to date, they have been a great help to pathophysiological studies as well as in the classification of complex clinical types and genotypes.[4]

CMT can be divided into several subtypes based on the causative gene, and the most common and typical subtype is CMT1A, the target disease of this clinical study. CMT1A develops due to the duplication of chromosome 17p11.2-p22 that contains peripheral myelin protein 22 (PMP22), and it is an autosomal dominant inheritance.[5] In electrophysiology tests, CMT1A is characterized by a uniform decrease in nerve conduction velocity. This is a characteristic of hereditary demyelinating neuropathy that contrasts with the conduction block and temporal dispersion shown in inflammatory demyelinating neuropathy.[6]

The onset age of patients with CMT1A is usually before 10 years of age, and the symptoms start in distal regions of limbs and progress to the proximal regions. As the disease progresses after typically manifesting first in the lower limbs, its symptoms are also shown in the upper limbs. Sensory loss, weakening of muscle strength, amyotrophy, etc., start to manifest in both feet as well as in the leg below the knees, and after several years, the symptoms also manifest in the hands and arms.[7]

Fats accumulate in the atrophied muscle tissues, and the fatty infiltration level within the muscles can be identified using MRI imaging. At this time, the fat content value (%) shall be measured and evaluated at one level for each muscle. [8]

The pathogenesis of CMT1A is known to be due to an increased quantity of mRNA caused by the duplication of the PMP22 gene, which in turn produces a structurally unstable myelin sheath.[9] It has been verified that the symptoms shown in mutated rats whose duplication of the PMP22 gene had been artificially induced were similar to those shown in humans.[10] [11] Demyelination of a nerve fiber occurs due to damages in a structurally unstable myelin sheath, and the nerve conduction velocity decreases because of this.

Numerous nonmyelinating or dysmyelinating Schwann cells are produced in CMT1A due to abnormal differentiation of immature Schwann cells, and thus cause a demyelinating neuropathy. A recent study has shown that the serum concentrations of p75 neurotrophin receptor (p75) and neural cell adhesion molecule 1 (NCAM) appear different depending on the

pathologic differences of Schwann cells in various peripheral neuropathies. Both NCAM and p75 are exosome proteins that are extracellularly secreted by immature Schwann cells. [12]

p62/seqestosome-1 (p62) is an autophagy receptor, which is essential in removing intracellular organelle or denatured protein using autophagy.[13] Functional change of inctracellular autophage occurs in various ways in many cellular environments. Schwann cells, which make peripheral nerve myelin, accumulate p62 due to the suppression of autophagy in a hereditary demyelinating disease environment.[14] Not only is the p62 level significantly higher in patients with inflammatory peripheral demyelination than in control, but a greater amount of serum p62 is observed in patients with hereditary peripheral demyelation disease (CMT1A) than in patients with inflammatory demyelination. In addition, the amount of p62 in CMT1A patient's serum is considered to be a very important serum indicator for CMT1A severity, as it is positively correlated with the duration of the disease and the decrease in motor neuron function.

In a separate retrospective biomarker study, we aim to evaluate the correlation between quantitative change of serum p62, p75 and NCAM and symptom changes in CMT1A patient group.

[figure not shown]

Figure 2 Pathophysiology of CMT

